#### 5.3. Procedures for Maintaining and Breaking the Masking

Under normal circumstances, the mask should not be broken until all subjects have completed the study and the database is finalized. Otherwise, the mask should be broken only if specific emergency treatment/course of action would be dictated by knowing the treatment status of the subject. In such cases, the investigator may, in an emergency, contact the medical monitor. In the event the mask is broken, the sponsor must be informed as soon as possible. The date, time, and reason for the unmasking must be documented in the subject record. The investigator is also advised not to reveal the study treatment assignment to the clinical site or sponsor personnel.

Subjects who are discontinued prior to the final evaluation may be replaced at the discretion of the study sponsor.

#### 6. STUDY INTERVENTION

#### 6.1. Identity of Test Articles

The following test articles will be used in this study:

Table 3: Test Articles	
------------------------	--

	Test	Control
Name	Investigational lubricating eye drop in a Novelia® bottle	Blink ® Tears
Manufacturer	Johnson and Johnson Surgical Vision	Johnson and Johnson Surgical Vision

	Test	Control
Ingredients	Boric Acid, Sodium Borate	Sodium Chlorite, Boric Acid,
	Dehydrate, Sodium Chloride,	Sodium Borate Dehydrate,
	Potassium Chloride, Calcium	Sodium Chloride, Potassium
	Chloride Hexahydrate,	Chloride, Calcium Chloride
	Polyethylene Glycol 400,	Hexahydrate, Polyethylene
	Magnesium Chloride	Glycol 400, Magnesium
	Hexahydrate, Sodium	Chloride Hexahydrate, Sodium
	Hyaluronate, Purified water	Hyaluronate, Purified water
Packaging form	Over-labeled	Over-labeled

With 45 subjects targeted to be enrolled in the study and each subject using 1 unit/bottle of eye-drops each; 45 units/bottles of each (90 in total) Test or Control articles are estimated to be used in the study.

#### 6.2. Ancillary Supplies/Products

The following solutions will be used in this study:

		Solution	
Solution name/ Description	Sclerafil (or other sponsor-approved product)	Fluorescein (or other sponsor-approved product)	Lacipure Saline Solution
Manufacturer	Bausch & Lomb	Akorn Inc.	Menicon
Preservative	None	None	Non-preserved
Other distinguishing items (dye, packaging, approval status, etc.)	N/A	D&C Yellow No. 8, 0.6 mg	N/A

Table 4: Ancillary Supplies

Sodium fluorescein dye will be used for biomicroscopy, as needed. Sterile, preservative free, saline may be used in this clinical study to rinse each eye.

#### 6.3. Administration of Test Article

Test articles will be dispensed to subjects meeting all eligibility requirements, including any application requirements set forth in this clinical protocol. This is not a dispensing study. The test articles will only be used in-office. The test articles will only be designated for clinic-only use.

#### 6.4. Packaging and Labeling

The test articles will be packaged in bottles as the primary packaging. The test article will be over-labeled to mask the subject to the identity of the eyedrops. The test articles will be in plastic bags as the secondary packaging form. The sample study label is shown below:

For Use in Clinical Study CR-6503 EYE DROPS CAUTION - For Investigational Use Only Use in accordance with the instructions provided Net Contents: 0.34 to 0.5 FL 0Z (10-15mL) STERILE Store at Room Temperature Sponsored by: Johnson & Johnson Surgical Vision, Inc. Irvine, CA 92618 USA LOT:ABC123 EXP: 2023/09/30 RC: S

#### 6.5. Storage Conditions

Test articles will be maintained at ambient temperatures at the clinical site. Test articles must be kept under secure conditions.

#### 6.6. Collection and Storage of Samples

When possible, any test article associated with an Adverse Event and/or a Product Quality Complaint must be retained pending directions from the sponsor for potential return to JJVC.

#### 6.7. Accountability of Test Articles

JJVC will provide the Investigator with sufficient quantities of study articles and supplies to complete the investigation. The Investigator is asked to retain all test article shipment documentation for the test article accountability records.

Test articles must be kept in a locked storage cabinet, accessible only to those assigned by the Investigator for dispensing. The Investigator may delegate this activity to authorized study site personnel listed on the Site Delegation Log. All test articles must be accounted. This includes:

- 1. What was dispensed in-office for the subject.
- 2. What was unused, including expired or malfunctioning product.
- 3. The number and reason for unplanned replacements.

The Investigator will collect all unused test articles from the subjects at the end of the subject's participation. Inoffice dispensed or used test articles must be discarded or at least separated from the clinical study inventory of un-dispensed test articles and must be labeled with the subject number and date of return, when retained. Following final reconciliation of test articles by the monitor, the Investigator or monitor will return all unused test articles to JJVC.

If there is a discrepancy between the shipment documents and the contents, contact the study monitor immediately.

#### 7. STUDY EVALUATIONS

#### 7.1. Time and Event Schedule

Table 52: Time and Events

Visit Information	Visit 1
	Screening, Baseline, In-office drop application
Time Point	Day 0
Estimated Visit Duration	3.0 hours
Statement of Informed Consent	X
Demographics	X
Medical History/Concomitant Medications	X
Screening Inclusion/Exclusion Criteria	Х
Eligibility after Screening	X
Entrance Distance Snellen Visual Acuity	Х
Baseline lens fit assessment	X
Biomicroscopy	Х
Eligibility after Baseline	X
Randomization	X

Visit Information	Visit 1
	Screening, Baseline, In-office drop application
Time Point	Day 0
Estimated Visit Duration	3.0 hours
Baseline LogMAR VA	X
Instillation of Drop#1	X
Ocular Symptoms	X
3-Minute Post drop #1 logMAR	X
10-Minute Post drop #1 logMAR	X
Lens fit assessment	X
90-minute washout	X
Instillation of Drop #2	X
Ocular Symptoms	X
3-Minute Post drop #2 logMAR	X
10-Minute Post drop #2 logMAR	X
Lens fit assessment	X
Exit Slit Lamp Evaluation	X
Exit Snellen VA	X
Final Evaluation	X

#### 7.2. Detailed Study Procedures

#### VISIT 1

The subjects must present to the visit wearing their habitual contact lenses.

	Visit 1: Screening					
Step	Procedure	Details				
1.1	Statement of Informed Consent	Each subject must read, understand, and sign the Statement of Informed Consent before being enrolled into the study. The Principal Investigator or his/her designee conducting the informed consent discussion must also sign the consent form. NOTE : The subject must be provided a signed copy of this document.				
1.2	Demographics	Record the subject's year of birth, age, gender, race and ethnicity.				
1.3	Medical History and Concomitant Medications	Questions regarding the subject's medical history and concomitant medications.				
1.4	Habitual Lenses	Questions regarding the subject's habitual lens type and parameters.				
1.5	Wear Time and Comfortable Wear Time with Habitual Lenses	Record the subject's wear time and comfortable wear time with their habitual contact lenses				
1.6	Eligibility after Screening	All responses to Screening Inclusion Criteria questions must be answered "yes" and all responses to Exclusion				

	Visit 1: Screening					
Step	Procedure	Details				
		Criteria must be answered "no" for the subject to be considered eligible.				
		If subject is deemed to be ineligible after screening, proceed to Final Evaluation and complete Subject Disposition. Refraction and Biomicroscopy forms are not required.				

5		Visit 1: Baseline	
Step	Procedure	Details	
1.7	Entrance Visual Acuity	Record the Snellen distance high contrast visual acuity to the nearest letter (OD, OS, and OU) with their habitual contact lenses in place.	
1.8	Baseline Subject Reported Ocular Symptoms	Subjects will respond to a verbal open-ended symptoms questionnaire.	
1.9	Habitual Contact Lens Fit Assessment	
 
Evaluate and grade lens centration, primary gaze movement, up-gaze movement, and tightness (push-up test).
 
The subject should not proceed to wear the lenses if any of the following is observed: 
 
presence of limbal exposure (appearance of clear cornea) in any gaze
 
presence of edge lift
 
presence of unacceptable movement (excessive or insufficient) in all three movement categories (primary gaze, upgaze, and push-up)
 
 
 
NOTE: If lens fit is unacceptable subject will be discontinued from the study.
 
	
1.10	Remove Habitual Contact Lenses	Remove habitual contact lenses and store in a case with non-preserved saline.	
1.11	Slit Lamp Biomicroscopy	The FDA slit lamp classification scale will be used to grade the findings and determine eligibility. If there are any Grade 3 or higher other slit-lamp findings, the subject is ineligible to continue at this time, but may return up to one additional time to determine eligibility. If discontinued a final examination must be completed. If there are no slit lamp findings, and the clearance of the fluorescein needs to be expedited, preservative- free saline may be instilled.	

	Visit 1: Baseline			
Step	Procedure	Details		
1.12	Expanded Sodium Fluorescein Corneal Staining	Corneal Staining Assessment (FDA grading scale) will be assessed using a more detailed scale for internal purposes only.		
1.13	Eligibility After Baseline	All responses to Inclusion Criteria questions must be answered "yes" and all responses to Exclusion Criteria questions must be answered "no" for the subject to be considered eligible.		
1.14	Re-insert Habitual Lenses	Habitual Lenses will be re-inserted.		
1.15	Settling Time	Allow habitual lenses 5 minutes to settle.		
1.16	Baseline Distance ETDRS LogMAR Visual Acuity	
 
Under high illumination and high chart luminance, record the distance (4 meter) ETDRS low contrast visual acuity OD (LC1) and OS (LC2). Note:
 
The room illuminance must be between 7.3 and 7.9 EV (394-597 lux).
 
Distance Low Contrast chart luminance acceptable range between 10.5 -10.7 EV (181-208cd/m^2)
 
		

	Visit 1: Treatment 1			
Step	Procedure	Details		
1.17	Randomization and Drop Selection	Assign the first study drop (Drop#1) based on the randomization schedule.		
1.18	Drop Instillation	The investigator will break the seal of drop #1 and discard the first drop. The investigator or technician will instill 1 drop in the right eye. Wait 1 minute and then instill 1 drop in the left eye.		
1.19	Subject Reported Ocular Symptoms	Subjects will respond to a verbal open-ended symptoms questionnaire.		
1.20	Drop Settling	Allow the drops to settle for 3 minutes (from OD drop #1 administration).		
1.21	3-minute Distance ETDRS LogMAR Visual Acuity (From OD Drop #1 Administration Time)	Under high illumination and high chart luminance, record the distance (4 meter) ETDRS low contrast visual acuity OD (LC3) and OS (LC4).		
1.22	10-minute Distance ETDRS LogMAR Visual Acuity (From OD Drop #1 Administration Time)	Under high illumination and high chart luminance, record the distance (4 meter) ETDRS low contrast visual acuity OD (LC1) and OS (LC2).		

	Visit 1: Treatment 1			
Step	Procedure	Details		
1.23	Habitual Contact Lens Fit Assessment Following the Application of Drop #1	
 
Evaluate and grade lens centration, primary gaze movement, up-gaze movement, and tightness (push-up test).
 
The subject should not proceed to wear the lenses if any of the following is observed: 
 
presence of limbal exposure (appearance of clear cornea) in any gaze
 
presence of edge lift
 
presence of unacceptable movement (excessive or insufficient) in all three movement categories (primary gaze, up-gaze, and push-up)
 
 
 
NOTE: If lens fit is unacceptable subject will be discontinued from the study.
 
		
1.24	Washout	Allow at least 90 minutes before continuing to the second drop as per the randomization schedule. (Subject will continue to wear their habitual lenses during this period.)		

	Visit 1: Treatment 2			
Step	tep Procedure Details			
1.25	Drop Instillation	The investigator will break the seal of Drop #2 and discard the first drop. The investigator or technician will instill 1 drop in the right eye. Wait 1 minute and then instill 1 drop in the left eye.		
1.26	Subject Reported Ocular Symptoms	Subjects will respond to a verbal open-ended symptoms questionnaire.		
1.27	Drop Settling	Allow the drops to settle for 3 minutes (from OD drop #2 administration).		
1.28	3-minute Distance ETDRS LogMAR Visual Acuity (From OD Drop #2 Administration Time)	Under high illumination and high chart luminance, record the distance (4 meter) ETDRS low contrast visual acuity OD (LC3) and OS (LC4).		
1.29	10-minute Distance ETDRS LogMAR Visual Acuity (From OD Drop #2 Administration Time)	Under high illumination and high chart luminance, record the distance (4 meter) ETDRS low contrast visual acuity OD (LC1) and OS (LC2).		

	Visit 1: Treatment 2			
Step	Procedure	Details		
1.30	Habitual Contact Lens Fit Assessment Following the Application of Drop #2	Evaluate and grade lens centration, primary gaze movement, up-gaze movement, and tightness (push-up test).		
		The subject should not proceed to wear the lenses if any of the following is observed:		
		
 
presence of limbal exposure (appearance of clear cornea) in any gaze
 
presence of edge lift
 
presence of unacceptable movement (excessive or insufficient) in all three movement categories (primary gaze, up-gaze, and push-up)
 
		
1.31	Remove Habitual Contact Lenses	Remove habitual contact lenses and store in a case with non-preserved saline.		

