#### **Exploratory endpoints:**

The exploratory endpoints in this study are:

- Slit lamp findings using FDA scale
- Snellen best corrected distance visual acuity
- Subject reported ocular symptoms
- Number of adverse events
- Number and reasons for discontinuation will be monitored
- Contact lens fitting assessment

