#### FINAL EVALUATION

The final evaluation will ordinarily take place immediately following the completion of all specified procedure during the visit per the study protocol. It may also take place at any point the subject discontinues the study or is terminated from the study.

	Final Evaluation			
Step	Step Procedure Details			
F.1	Final Exam Form	Indicate if the subject completed the study successfully. If subject discontinued from the study, indicate the reason.		
F.2	Exit Slit Lamp Biomicroscopy	

FDA Slit Lamp Classification Scale will be used to grade the findings.

If the clearance of the fluorescein needs to be expedited, preservative-free rewetting drops or saline may be instilled. This step is not necessary if the subject was exited due to screen failure.

		
F.3	Expanded Sodium Fluorescein Corneal Staining	Corneal Staining Assessment (FDA grading scale) will be assessed using a more detailed scale for internal purposes only.		
F.4	Exit Distance Visual Acuity	Record the distance high contrast visual acuity to the nearest letter (OD, OS, and OU) with their habitual spectacle/contact lens correction in place.		

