#### 7.3. Unscheduled Visits

If, during the investigation, a subject requires an unscheduled visit to the clinical site, the following information will be collected, as appropriate:

• Chief complaint prompting the visit. If the reason is an adverse event, the applicable eCRF for the adverse event must be completed and subject record completed as appropriate.

- Date and time of the visit and all procedures completed at the unscheduled visit.
- Review of adverse event and concomitant medications.
- Documentation of any test article dispensed or collected from the subject, if applicable.
- Slit lamp findings (using the Slit Lamp Classification Scale).

If the Investigator withdraws a subject from the study, the final study visit case report forms must be completed indicating the reason(s) why the subject was withdrawn. The subject record must be completed documenting the date and primary reason for withdrawal and the study CRA notified.

Any ocular and non-ocular Adverse Events that are ongoing at the time of the study visit will be followed by the Investigator, within licensure, until they have resolved, returned to pre-treatment status, stabilized, or been satisfactorily explained. If further treatment i.e., beyond licensure is required, the subject will be referred to the appropriate health care provider.

	Unscheduled Visit				
Step	Step Procedure Details				
U.1	Reason for unscheduled visit	Specify the reason for the visit.			
U.2	Chief Complaints	Record the subject's chief complaints for reasons for the unscheduled visit.			
U.3	Adverse Events and Concomitant Medications Review	Review any changes to the subject's medical history or concomitant medications from the previous study visit. Record any changes, and any adverse events.			
U.4	Entrance Visual Acuity	Record the entrance distance visual acuity (OD, OS, and DU) to the nearest letter.			
U.5	Subjective Sphero- cylindrical Refraction	Perform bare-eye subjective spherocylindrical refraction with a phoropter (adopt the maximum plus to maximum visual acuity (MPMVA) approach and use the duo-chrome test for binocular balancing) and record the best corrected distance visual acuity to the nearest letter (OD, OS).			
U.6	Slit Lamp Biomicroscopy	FDA Slit Lamp Classification Scale will be used to grade the findings. If the clearance of the fluorescein needs to be expedited, preservative-free saline may be instilled.			

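### No symptom question is scheduled beyond about the first 3 minutes after each drop, and the only planned visit lists no adverse-event enquiry

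*Combined protocol and SAP*

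**What the plan says.** Section 7.2 fixes the order of events for each drop. The right eye is treated first, and then staff are told: "Wait 1 minute and then instill 1 drop in the left eye". The symptom step follows at once (1.19 for Drop #1, 1.26 for Drop #2): "Subjects will respond to a verbal open-ended symptoms questionnaire". Next comes settling, timed from the right-eye drop: "Allow the drops to settle for 3 minutes (from OD drop #1 administration" in period 1 and "Allow the drops to settle for 3 minutes (from OD drop #2 administration" in period 2. The 3-minute reading, the 10-minute reading and the lens-fit check come after that. The interval between drops is set by step 1.24: "Allow at least 90 minutes before continuing to the second drop as per the randomization schedule". Table 5 in section 7.1 shows the same order.

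The only other symptom question is the baseline one at step 1.8. It precedes lens removal, slit lamp, fluorescein staining, lens re-insertion and the baseline logMAR reading.

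The Final Evaluation opens with F.1: "Indicate if the subject completed the study successfully". If the subject did not, the reason is recorded. F.2 to F.4 are slit lamp, corneal staining and acuity. An adverse-event and concomitant-medication review appears only at step U.3 in section 7.3, for unscheduled visits: "Record any changes, and any adverse events".

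Section 2.2 lists subject-reported ocular symptoms and "Number of adverse events" among the exploratory endpoints, and section 14.7 plans summary statistics for both.

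**The concern.** Two listed endpoints depend on what subjects say, and subjects are asked only within the first few minutes after each drop. The primary hypothesis concerns 10 minutes, but no one is asked at that time how the eye feels. Section 1.4 names, as a risk of artificial tears, comfort falling below what it was when the drop first went in. That effect develops after instillation, and a question at minutes 1 to 3 is poorly placed to detect it.

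Attribution is a second problem. With no question just before Drop #2, a complaint at step 1.26 might belong to Drop #2, be left over from Drop #1, or reflect lens wear during the washout. Step 1.8 is not an immediate pre-drop reference for either drop.

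For adverse events, the study is a single visit and the only prompted review is reserved for unscheduled visits, which most subjects will not have. Section 9 also says that concomitant medications are updated during the study, but no scheduled step after 1.3 does this. At stake is how a finding of few symptoms could be read in a study meant to support EU registration for use with contact lenses.

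**Working it through.** The plan states no symptom or adverse-event rate, so it has no figure of its own to reproduce on this point. The sample size and power in section 14.2 do not enter. The check is a reading of the schedule, then simple arithmetic on its minutes.

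**Schedule, in minutes from the right-eye drop**
- 0: right-eye drop (1.18, 1.25).
- 1: left-eye drop.
- About 1 to 3: symptom question (1.19, 1.26), which is 0 to 2 minutes after the left-eye drop.
- 3: first logMAR reading (1.21, 1.28).
- 10: second logMAR reading (1.22, 1.29), then lens fit (1.23, 1.30). No question is listed.
- Washout of at least 90 minutes after Drop #1 (1.24). No question is listed during it or at its end.
- After Drop #2: lens removal (1.31), then F.1 to F.4. No symptom or adverse-event question is listed.

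**Share of time covered by the question**
- Drop #1 is the most recent drop for at least 10 + 90 = 100 minutes. Counting minutes 1 to 3: 2/100 = 2%. Counting from minute 0: 3/100 = 3%.
- Drop #2 has at least 10 minutes to its last acuity reading. On the same two counts: 2/10 = 20% and 3/10 = 30%, the latter at most, since exit procedures follow.

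These are shares of clock time, not of symptoms.

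**Illustration under assumed rates.** Let r be the proportion of subjects whose symptom with a given drop starts only after the question. With 38 completers, the expected number not asked about is 38r, and the chance of at least one is 1 − (1 − r)^38.
- r = 2%: 38 × 0.02 = 0.8 subjects per drop; 1 − 0.98^38 = 54%.
- r = 5%: 38 × 0.05 = 1.9; 1 − 0.95^38 = 86%.
- r = 10%: 38 × 0.10 = 3.8; 1 − 0.90^38 = 98%.

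The rates are assumptions. The rows show only that even a low late-onset rate would probably leave someone unasked.

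**Adverse events.** Section 13.3 starts recording at exposure and requires every event during enrolment to be documented, whatever its cause. Set beside 7.1 and 7.2, it gives a duty to record but no scheduled question to elicit. It also asks for a diagnosis rather than a symptom, and leaves events reported after exit to the investigator's discretion. A transient late symptom thus has no scheduled route into the symptom endpoint and only a weak one into the adverse-event count.

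**The case against.** The strongest reply is that the plan observes far more than the symptom question. Acuity is measured at 10 minutes in each eye after each drop, so blur is covered by the primary measurement itself. Lens fit is graded after each drop, and slit lamp, staining and acuity follow at exit. This stands, and it narrows the gap mainly to subjective discomfort. The exit slit lamp and staining come after both drops, however, so they cannot easily assign a finding to one.

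A reader might infer that later events drop out of the adverse-event endpoint altogether. The documents do not support that: section 13.3 requires them to be recorded, and those volunteered or found on examination count. For the same reason, one might argue that zero events in 45 subjects, with a one-sided 95% upper bound of 1 − 0.05^(1/45) = 6.4%, would apply only to the first 3 minutes. That does not hold for adverse events, whose recording has no such time limit.

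It is also fair to say that both drops are questioned at the same point and the order is randomised, so no bias in favour of one product is shown. That stands. If one drop did leave lingering complaints, though, those voiced at step 1.26 would be counted against the other drop, which blurs the comparison.

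Finally, Appendix D includes a work instruction on subject-reported symptoms whose text is not visible. It may set a recall period, onset recording or repeat questioning. The point therefore rests on the visible schedule alone; neither Table 5 nor section 7.2 shows a repeat.

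**Conclusion.** The point holds in a limited form. As the visible schedule stands, the exploratory symptom endpoint describes about the first 3 minutes after each drop, and a complaint after Drop #2 has no immediate pre-drop reference. Adverse-event capture is passive rather than closed: it relies on spontaneous report and later examinations, so symptom-only events may be under-counted. Site staff know which drop is in use (section 5.2), so informal probing could differ between drops; a scripted question would reduce that risk.

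The amount of under-counting cannot be estimated from the documents. The 2% to 3% is a share of time, and the subject counts rest on assumed rates. The conclusion also assumes that the Appendix D instruction adds no later question. Both endpoints are exploratory with summary statistics only, and the primary endpoint, its analysis and the sample size are untouched. Severity is minor; this is a cheap improvement.

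**What to change.** Keep steps 1.19 and 1.26. Then:
- Repeat the same open-ended question right after the 10-minute readings (after 1.22 and 1.29) and once at the end of the washout, just before 1.25. Record the onset time and the last drop given.
- Add an adverse-event and concomitant-medication review, worded as in U.3, to the Final Evaluation and as a row in Table 5.
- State in section 14.7 that symptoms will be summarised by drop and time point.
- Check the Appendix D symptom instruction so that it and section 7.2 agree on timing.

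The cost is protocol wording, a few eCRF fields and a minute or two of questions per subject, by the same staff in the same visit. Reported symptom counts, and possibly adverse-event counts, may rise slightly. Because adverse events are entered as diagnoses, the added symptom questions will mainly inform the symptom summary; the review at the Final Evaluation is the part that serves the adverse-event count.
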